For the UK drug utilization and cohort study, we will make use of anonymised primary care data. In the period January 2012- December 2015, women between the ages 18-49 years who have been registered for at least two years prior with one of the general practices that contributed data to The Health Improvement Network (THIN) primary care database will be included. New and prevalent users will be identified. In addition, information is available on social deprivation, body mass index (BMI) and smoking status which can be used to stratify patients on the risk of VTE.

Study size:

In 2014, approximately 1.4 million women between 15-50 years used oral contraceptives in the Netherlands, of whom ~1.3 million are registered in the SFK. In women between 15-25 years, the majority of oral contraceptive users will be starters (the new users in our study will include these starters as well as women who have used CHC in the past, but not in the previous two years). Data from the CBS indicated, that in 2014, there were 1 011 127 women between 15-25 years, of whom ~59% were using oral contraceptives (n=596 565). From unpublished data from the department of Clinical Epidemiology, Leiden University, we estimate that in 2-year period, approximately 16% of premenopausal women switch from one oral contraceptive agent to another. With 1.3 million oral contraceptive users, this indicates ~212 000 switches per 2-year period.

As mentioned above, the number of women between 15-25 years using CHCs in 2014 is 596 565. This number will vary in the other years of the study period. From literature it is known that the risk of VTE is increased 8-fold among starters in the first year of use (in the first three months, the risk is increased 13x) (3). However, this risk differs for the different types of CHCs. Also the proportion of each generation of CHC will differ in each observation window. Therefore, it is difficult to estimate the number of cases of VTE in new users of CHC in the study period January 2012- December 2015.

In Denmark, annually more than 330 000 women receive CHC (<https://laegemiddelstyrelsen.dk/da/udgivelser/2016/~-/media/CD29697BD25C4642968D9386979472A9.ashx>; <http://medstat.dk/>). The annual incidence rate of VTE is about 4 per 10 000 for women of reproductive age not using oral contraceptives. Thus, a conservative estimate for 4 years of follow-up assuming the size of the study population of 300 000, is at least 480 cases of

VTE (4).

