Delivery of manuscript	01-05-2018

7. Rationale and background

Venous thromboembolism (VTE) in young women is rare, with an annual incidence of approximately 2-5 per 10 000 women (6). An increased risk of VTE associated with oral contraceptive use has long been established and while the absolute risk of VTE in young women is low, the fact that millions of women worldwide are using oral contraceptives indicates that these preparations are responsible for a large number of cases of VTE

(3, 7-11). Several large studies including a review in 2013 by the European Medicines Agency (EMA) concluded that the risk of VTE associated with hormonal contraceptive preparations which contained gestodene, desogestrel, or drospirenone was increased compared with hormonal contraceptive preparations containing levonorgestrel (1, 5, 12, 13).

After the publication of the review by the EMA, the European Commission adopted on 16 2014, a legally binding decision to update the product information of all combined hormonal contraceptives (CHC) throughout the European Union. This included information to patients: awareness of factors that increase the risk of VTE and information to health care professionals: the type of CHC with the lowest VTE risk (levonorgestrel, norethisterone, or norgestimate) and the fact that CHC are contraindicated in the presence of one serious or multiple risk factors for VTE. It is currently unknown whether the publication of this review led to a change in prescription patterns and a subsequent change in the incidence of VTE in young women.

The aim of this study is therefore to investigate the CHC utilisation and prescribing patterns in a sample of Three European Union Member states (Denmark, United Kingdom, and the Netherlands) in a time period including the completion of the 2013 review and implementation of the resulting recommendations and to estimate any changes in the incidence of VTE between the two periods specified.

This study will provide evidence regarding the necessity of the recommendation to use safer oral contraceptive preparations, as it will show whether the implementation of the recommendation was successful and whether it actually affected the incidence of VTE in the target population.

8. Research question and objectives

Was there a change in CHC prescribing patterns between the periods January 2012 – January 2014 and February 2014 – December 2015 and, if so, was there a subsequent change in the incidence rate of VTE?

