Medication use in the SFK database will be used to approximate the occurrence of VTE by using the first dose of oral anticoagulant, which, in case of DOAC use is specific for VTE or the duration of treatment with Vitamin K antagonists. Incidence of VTE is calculated by following the new users of CHC within each calendar window until they experience a VTE, or up to one year.

We will calculate the incidence among the new users of oral contraceptives in general and per type of oral contraceptive (different types and grouped by generation (second, third and newer generations)).

Analysis

We will tabulate the estimates of the annual incidence of VTE including 95% confidence intervals for each calendar window of the study period.

From segmented regression analysis (WP1), we will obtain information on a potential change in the proportion of initiators of each generation of CHC between January 2012-January 2014 and February 2014- December 2015. Since we have information about the prescription patterns among new users, we can assess whether the changes observed in the proportions of each generation is associated with changes in the incidence rate of VTE in women initiating oral contraceptive use.

Furthermore, we can study the changes in the incidence of VTE within users of different types (and generations) of oral contraceptives. A change in this incidence over time, may indicate that certain preparations are prescribed to low/high risk individuals.

Because we have information about the age and socioeconomic status (risk factors of VTE) of these women, we can stratify analyses on these factors.

For our analysis we will use SPSS for Windows, release 23.0.

WP5

Objectives

To assess changes in the incidence rates of VTE among women of reproductive age overall and by CHC-initiation/switching in Denmark between January 2012-January 2014 and February 2014-December 2015.

Study population

For each calendar year of the study period (1 January 2012 to 31 December 2015) we will identify women who were between 18 and 49 years old. Individuals with no previous record of VTE prior to study entry (from 2002 onwards) will be followed until they are recorded with a VTE, become 50 years of age, 31st of December 2015 or they migrate.

Analysis

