We will estimate the incidence rates of VTE by 10 000 person years at risk in CHC-initiators/switchers before and after the EMA recommendation, including 95% confidence intervals for each calendar year of the study period. We provide overall estimates as well as estimates stratified by age at CHC initiation in oral contraceptive initiators.

For each observation window period (January 2012- January 2014 and between February 2014-December 2015) we will compare the age-standardised incidence rates of VTE against the age standardized VTE incidence rates among initiators/switchers of oral contraceptives in order to evaluate whether overall changes in CHC use is associated with overall changes in incidence of VTE.

Analyses will be performed using SAS version 9.2 or higher.

WP6

Objectives

To assess the incidence rate of VTE among women of reproductive age overall and by initiated CHC in United Kingdom between January 2012- December 2015.

Study population

For the estimate of incidence of VTE in CHC users in UK we will make use of anonymized primary care data. For each calendar year of the study period (1 January 2012 to 31 December 2015) we will identify women who were between 18 and 49 years and have been registered for at least two years prior with one of the general practices that contributed data to THIN. Individuals initiated on CHC with no previous record of VTE prior to study entry (from 2002 onwards) will be followed up until they have their first record of VTE, they become 50 years of age, 31 December 2015 or they de-register with the general practice, whichever comes first.

Analysis

We will tabulate the estimates of incident VTE by 10 000 person years at risk including 95% confidence intervals for each calendar year of the study period among women using CHCs of reproductive age in UK. We provide overall estimates as well as estimates stratified by age, social deprivation (Quintiles of Townsend Deprivation scores), BMI and smoking status.

For each observation window period (January 2012- January 2014 and between February 2014- December 2015) we will calculate the incidence among the new users of oral contraceptives in general and per type of oral contraceptive (different types and grouped by generation (second, third and newer generations)).

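### In WP5, searching for prior VTE from a fixed 2002 start gives the later window a longer known VTE-free history and tilts the overall Danish rate slightly downward

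*Protocol*

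**What the plan says.** Section 9.2, WP5, Study population, identifies women by year: "For each calendar year of the study period (1 January 2012 to 31 December 2015) we will identify women who were between 18 and 49". It then sets the prior-VTE rule: "Individuals with no previous record of VTE prior to study entry (from 2002 onwards) will be followed until they are recorded with a VTE". The other ends of follow-up are the 50th birthday, the end of 2015 and migration.

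The WP5 analysis works by window, "For each observation window period (January 2012- January 2014 and between February 2014-December 2015", and sets "age-standardised incidence rates of VTE against the age standardized VTE incidence rates among initiators/switchers of oral contraceptives" side by side. The overall rate in all women of this age is thus one of the quantities compared over time.

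WP6 uses the same calendar start for the UK, but only among CHC starters: "Individuals initiated on CHC with no previous record of VTE prior to study entry (from 2002 onwards".

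For new CHC use the protocol does otherwise: it sets a look-back of constant length, two years before the prescription. It sets no constant length for VTE history, and section 9.5 (Limitations) does not mention the point.

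**The concern.** A fixed start date combined with moving study time makes the outcome definition stricter as the study proceeds. In January 2012 a woman counts as VTE-free if nothing was recorded for 10 years; in December 2015 the record covers almost 14. Women are eligible up to age 49, so many had adult years before 2002 that the search cannot see. If such a woman had a VTE then and has a recurrence in the study period, it is counted as incident. This unseen group gets no new members among long-term residents, and it shrinks as women turn 50 or have a recurrence recorded.

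The study asks whether VTE incidence changed after the Commission decision. A definition that yields fewer counted events in the second window pushes the answer towards a decline, which would be read as benefit.

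**Working it through.** **The plan's own figure.** Section 4, Study size, gives for Denmark "The annual incidence rate of VTE is about 4 per 10 000 for women of reproductive age not using oral contraceptives" and, for "4 years of follow-up assuming the size of the study population of 300 000, is at least 480 cases of" VTE: 300 000 × 4 × 4/10 000 = 480. This reproduces.

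**Look-back (date minus 1 January 2002).**
- 1 January 2012: 10.0 years
- end of January 2014: 12.1 years
- 31 December 2015: 13.996 years
- window midpoints: 11.04 and 13.04 years, a difference of 2.0

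**Model.** Assumptions not in the documents: risk of first VTE starts at age 15, ages are uniform from 18 up to 50, and late recurrence is a constant *rec* of 1-3% per year.

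For age a at time t, unseen years are U = max(0, a − (t − 2002) − 15). With a first-VTE rate that is flat by age, that rate cancels (so it does not matter where it lies in section 7's "annual incidence of approximately 2-5 per 10 000 women"), and

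spurious rate ratio = (1 + rec × U2) / (1 + rec × U1),

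where U1 and U2 are averages over ages and over each window. If the rate rises with age, U is replaced by the cumulative unseen rate divided by the mean current rate.

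| First-VTE rate by age | U1 | U2 | rec 1% | rec 2% | rec 3% |
|---|---|---|---|---|---|
| Flat | 8.974 | 7.539 | 0.9868 | 0.9757 | 0.9661 |
| Doubles per 10 years | 3.73 | 2.95 | 0.9925 | 0.9855 | 0.9790 |
| Triples per 10 years | 2.07 | 1.56 | 0.9950 | 0.9902 | 0.9856 |

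Example, flat at 2%: (1 + 0.02 × 7.539)/(1 + 0.02 × 8.974) = 1.1508/1.1795 = 0.976. Over the table the spurious fall runs from 0.5% to 3.4%. Removing women whose recurrence was already recorded since 2002 leaves the flat-rate ratios at 0.987, 0.976 and 0.966. In that version, 0.5% per year gives 0.993 and 5% gives 0.951.

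**Does age standardisation help?** Flat rate, rec 2%, by age band: 18-24, 1.000; 25-29, 0.977; 30-34, 0.965; 35-39, 0.967; 40-44, 0.970; 45-49, 0.972. A standardised rate is a weighted mean over bands. Every band from 25 upward is biased the same way, so no weighting removes the bias. At 18-24 it vanishes because the oldest of these women were about 15 in January 2002.

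**Does an equal look-back help?** With 10 years of history required at each 1 January, all nine cells of the table move to 0.999-1.000. In the flat 3% case, recurrences make up 22.0% and 21.9% of counted events in the two windows, against 21.2% and 18.4% under the 2002 rule. Contamination is equalised, not removed.

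**Against random error.** Splitting 480 cases by 25 and 23 months gives 250 and 230. The standard error of the log rate ratio is √(1/250 + 1/230) = 0.0914, so the 95% interval around 1 is 0.84 to 1.20. The 480 comes from a population sized on CHC recipients, so an all-women analysis has more cases. With four times as many (1 920, an assumption), the standard error halves to 0.0457 and the interval is 0.91 to 1.09.

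**The case against.** The size is not a document figure. Recurrence, age at first VTE and the share of women with VTE before 2002 are all assumed, and the upper end of the range needs a VTE rate that is flat from age 15. With a steep age gradient the fall is only 0.5-1.4%. This stands, and is why a range is given.

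The analyses closest to the research question are little affected. Section 7 says CHC are contraindicated with one serious or multiple VTE risk factors, so few women with an earlier VTE should be among initiators or switchers. This stands too: the point bears on the overall Danish rate.

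Using all recorded history is a defensible way to define a first VTE. True for a single rate, less so for a comparison of two periods with unequal history. Nor does it help that most women enter on 1 January 2012 with the same 10 years: follow-up stops at the first VTE, so known VTE-free history still lengthens with calendar time. Immigrants with unrecorded earlier VTE could offset part of the drift; the documents give no means of sizing this.

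Two stronger readings are tempting. A reader might infer that the drift is as large as any real effect. With 28% use and rates of 2, 6 and 10.5 per 10 000 (mean 8 in users), moving 10 points of users to lower-risk products lowers the all-women rate by 0.28 × 0.10 × 4.5/(0.72 × 2 + 0.28 × 8) = 0.126/3.68 = 3.4%. But the 10 points are arbitrary (20 or 30 give 6.8% or 10.3%), the 28% is a UK figure for oral contraceptives, and the user mean needs a product mix the protocol does not state. A reader might also infer that UK history can be as short as the two-year registration minimum and drifts likewise. The protocol does not say that earlier diagnoses are missing from a newly registered woman's record, and the minimum is the same in both windows.

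**Conclusion.** The point holds for one comparison: the overall Danish VTE rate in women aged 18-49 between the two windows. The 10-to-14-year growth follows from the text. The downward direction follows from it too, apart from the possible immigrant offset. The size, about 0.5-3.4%, rests on assumed recurrence of 1-3% per year and on the assumed age gradient. It is near zero at ages 18-24, smaller in CHC initiators and switchers and in WP6, and probably inside the study's random error. It is a minor defect worth correcting because it is systematic, favours the expected answer and is cheap to remove. It does not show that an observed Danish decline would be an artefact, and the documents do not support calling it comparable to the true effect.

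**What to change.** In WP5, for the between-window comparison of overall rates:

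- Apply the same 10-year VTE look-back at the start of each calendar year. Applying it only at cohort entry would not cure the drift.
- Keep the rule that uses all history from 2002 as a companion analysis.
- Report the overall comparison separately for ages 18-24, where history is nearly complete. At present WP5 stratifies by age only among initiators.

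Leave WP6 as it is: cutting its history to one common length could increase misclassification, and no drift has been shown there.

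The cost is one date rule in the Danish program and one extra table. The downside is that a few later-window women with a VTE more than 10 years earlier are readmitted, so contamination becomes equal between windows but does not disappear. The companion analysis shows how much this matters.

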A previous UK primary care database study estimated the crude incidence rate of VTE cases per 10 000 women years was 5.9 (95% confidence interval 5.7-6.0) in CPRD and 6.1 (6.0- 6.3) in QResearch (5). In UK around 28% use oral contraceptives and CHC form a substantial proportion of these.

Data analysis:

In order to assess the effects of the review on initiation (new use) as well as on switching of treatment (between January 2012- January 2014 and between February 2014- December 2015), we will perform segmented regression analyses.

For the Dutch part of study, we will calculate the incidence of VTE among the new users of CHC within each calendar window (January 2012- January 2014 and February 2014- December 2015). From segmented regression analysis, we will obtain information on a potential change in the proportion of different types of oral contraceptives in new users separately and grouped according to generation of CHC after the European commission decision (January 2014). Since we have information about the prescription patterns among new users, we can assess whether the changes observed in the proportions of use of each generation is associated with changes in the incidence rate of VTE in women initiating oral contraceptive use. Furthermore, we will study the changes in the incidence of VTE within users of different types (and generations) of CHCs. A change in this incidence over time, may indicate that certain preparations are prescribed to low/high risk individuals. We will stratify analyses on age and socioeconomic status (risk factors of VTE) of the women.

For the Danish and UK part of the study, estimates on the incidence of VTE will be calculated. Overall estimates as well as estimates stratified by risk factors such as age, socio-economic status, BMI (UK only), smoking status (UK only) will be provided. For the Danish and UK data we will compare the age-standardised incidence rates of VTE against the age standardised initiations of oral contraceptives in order to evaluate whether overall changes in CHC use is associated with overall changes in incidence of VTE.

Milestones:

Task	Month
Data extraction and analysis	10
Writing study results for the EMA	3
Writing manuscript for submission to peer-reviewed journal	3

5. Amendments and updates

None

6. Milestones

Milestone	Planned date
Start of data collection (extraction)	31-03-2017
End of data collection (extraction)	31-12-2017
Final report of study results	01-05-2018

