WP4 The Netherlands. For the calculation of the incidence rate of VTE between the two periods specified, i.e. January 2012 to January 2014 and February 2014 to December 2015, we will analyse new users of CHCs (within each calendar window) and assess whether they will develop VTE within one year of CHC initiation. From the analysis of WP1, we will obtain information on a potential change in the proportion of initiators of each generation of CHC between January 2012- January 2014 and February 2014- December 2015. Since we have information about the prescription patterns among new users, we can assess whether the changes observed in the proportions of each generation is associated with changes in the incidence rate of VTE in women initiating oral contraceptive use. Furthermore, we can study the changes in the incidence of VTE within users of different types (and generations) of oral contraceptives. A change in this incidence over time, may indicate that certain preparations are prescribed to low/high risk individuals. Because we have information about the age and socioeconomic status (risk factors of VTE) of these women, we can stratify analyses on these factors.

WP5 Denmark. Incidence rate of VTE will be estimated from the routinely recorded data based on validated algorithms. VTE will be measured using discharge diagnoses recorded in the Danish National Patient Registry.

WP6 United Kingdom. Incidence rates of VTE will be estimated from the routinely recorded data. VTE will be measured by using diagnoses entered into the electronic primary care records by Read codes. It is a hierarchical classification system, linked to the International Classification of Diseases (ICD 10), but more comprehensive.

WP7 Combining findings from WP1-6 to report on trends in oral contraceptive use in the periods before and after the publication of the 2013 EMA review, i.e., January 2012 – January 2014 and February 2014 – December 2015, and the associated changes in the incidence of VTE in the two periods. These results will be combined in the final report for the EMA and in the manuscript for submission for publication.

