We will consider each CHC individually and, additional to the analysis of individual types of combined oral contraceptives, in our analysis, we will group CHC together according to generation (i.e., the second generation containing levonorgestrel/norgestimate and ethinylestradiol, the third generation containing gestodene/desogestrel and ethinylestradiol and the newer generations containing drospirenone and ethinylestradiol).

Analysis

For each calendar year, we provide estimates of the proportion of each oral contraceptive type and the number of switchers (from one type to another or to a different pill strength) overall and stratified by age at initiation of CHC (18-24, 25-29, 30-34, 35-39, 40-44 and 45-49 years).

We will estimate incidence rates of initiating CHC use per 1000 person years at risk including 95% confidence intervals for each calendar year using incident dispensation as the indicator of CHC initiation. Similarly, we will provide estimates of incidence rates of switching per 1000 person years at risk including 95% confidence intervals for each calendar year of the study period.

In order to assess the effects of the review on initiation as well as on switching of treatment (between January 2012- January 2014 and between February 2014- December 2015), we will perform segmented regression analysis, taking the two time periods into account.

For our analyses we will be using SAS version 9.2 or higher.

WP3

Objectives

To obtain the number and proportion of women initiating different types of oral contraceptives in UK between January 2012 to December 2015 and to investigate switching pattern using data from The Health Improvement Network (THIN) primary care database.

Methods

Study population

For the UK drug utilization study, we will make use of anonymised primary care data from when women consult their general practice to obtain oral contraceptives. For each calendar year of the study period (1 January 2012 to 31 December 2015) we will identify women who were between 18 and 49 years and have been registered for at least two years prior with one of the general practices that contributed data to THIN. Individuals with no oral contraceptives prescription prior to study entry (from 2010 onwards) will be followed up until they receive their first oral contraceptive prescription, they become 50 years of age, 31 December 2015, or leave the practice. The new users are defined as women with no prior prescription of CHC in the two years before.

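### The Danish (WP5) association step compares VTE rates with VTE rates, so neither the level nor the mix of CHC use enters, and it conflicts with the abstract

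*Protocol*

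**What the plan says.** The WP5 analysis in section 9.2 states that, for each of the two windows, "we will compare the age-standardised incidence rates of VTE against the age standardized VTE incidence rates among initiators/switchers of oral contraceptives". It gives the purpose as "in order to evaluate whether overall changes in CHC use is associated with overall changes in incidence of VTE".

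The abstract (section 4, Data analysis, Danish and UK part) gives the same purpose but a different comparator: "we will compare the age-standardised incidence rates of VTE against the age standardised initiations of oral contraceptives".

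The measure of use that the abstract calls for is available from the Danish drug utilisation package. WP2 says "We will estimate incidence rates of initiating CHC use per 1000 person years at risk", and for the product mix it says "we will group CHC together according to generation". WP7 in section 9.1 then combines WP1 to WP6 to report trends in use "and the associated changes in the incidence of VTE in the two periods".

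For VTE strata, WP5 in section 9.2 says "We provide overall estimates as well as estimates stratified by age at CHC initiation in oral contraceptive initiators". WP4 goes further and plans incidence "per type of oral contraceptive (different types and grouped by generation (second, third and newer generations"; WP6 plans the same.

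**The concern.** The WP5 sentence announces an evaluation of one change (CHC use) against another (VTE incidence), but names two quantities that are both VTE incidence. One is the rate in all women; the other is the rate in initiators and switchers, who are part of all women. The comparison is also set up within each window, whereas the stated purpose concerns change from one window to the next.

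Objective 4 asks for exactly this association, and WP5 is the Danish VTE package. WP4 and WP6 each take the change in generation proportions from their own country's segmented regression and set it against the change in VTE incidence. WP5 makes no such reference to WP2. An analyst who follows section 9.2 to the letter would produce a comparison that cannot answer the question attached to it.

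**Working it through.** **1. The one Danish figure the plan states.** Abstract, Study size: 300 000 women × 4 years × 4/10 000 per year = 480 cases. This reproduces. The point does not depend on it.

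**2. The two versions of the Danish step.**

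| | One side | Other side | Measure of use? |
|---|---|---|---|
| Abstract, Data analysis | age-standardised VTE incidence | age-standardised initiations | yes |
| Section 9.2, WP5 | age-standardised VTE incidence | age-standardised VTE incidence in initiators/switchers | no; use only defines the group |

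**3. Can the WP5 pair of rates tell changed use from unchanged use?** Write all-women rate = p × user rate + (1 − p) × non-user rate, per 10 000.

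Inputs:
- p = 28% is the abstract's UK oral contraceptive share. It is an assumption here, because no Danish share is given.
- User rate 8 and non-user rate 2 lie within the abstract's risk table.
- All users stand in for initiators/switchers, which is also an assumption.

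Results:
- Window 1: 0.28 × 8 + 0.72 × 2 = 3.68.
- Case A, window 2, use falls to 23% and rates are unchanged: 0.23 × 8 + 0.77 × 2 = 3.38.
- Case B, window 2, use stays at 28% and the non-user rate falls: (3.38 − 0.28 × 8)/0.72 = 1.58 gives 3.38 again.

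WP5 would see (all women, users) move from (3.68, 8) to (3.38, 8) in both cases, although use fell only in A.

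**4. Range of assumptions** (same p, 28% to 23% in case A).

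| User rate | Non-user rate | All women, window 1 → 2 | Case B non-user rate |
|---|---|---|---|
| 6 | 2 | 3.12 → 2.92 | 1.72 |
| 8 | 2 | 3.68 → 3.38 | 1.58 |
| 10.5 | 2 | 4.38 → 3.955 | 1.41 |
| 8 | 4 | 5.12 → 4.92 | 3.72 |

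An unchanged-use scenario with the same pair exists in every row.

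**5. Product mix.** Take midpoints of the risk table, 6 for the 5–7 group and 10.5 for the 9–12 group, with non-users at 2, and assume 30% users.
- Half of users on the lower-risk group: user rate 0.5 × 6 + 0.5 × 10.5 = 8.25; all women 0.3 × 8.25 + 0.7 × 2 = 3.875.
- Three quarters on the lower-risk group: user rate 0.75 × 6 + 0.25 × 10.5 = 7.125; all women 0.3 × 7.125 + 0.7 × 2 = 3.54.
- Mix unchanged, but the risk of every product multiplied by 7.125/8.25 = 0.864: again 7.125 and 3.54.

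A shift towards safer products and no shift at all can give the same two VTE rates.

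**The case against.** The strongest reply is that this is a drafting slip with little consequence. The abstract states the right comparator, WP2 plans Danish initiation and switching rates, generation groups and segmented regression, and WP7 brings the packages together. Much of this stands. A reader might infer that Denmark cannot address Objective 4 at all, and the protocol does not support that: the ingredients are planned and can be set side by side. But WP7 states no method of association, so nothing downstream corrects the WP5 sentence, and section 9.2 is where an analyst will look.

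A second reply is that use does enter, because one group is defined by initiating or switching, and its VTE rates may show whether a change appears in exposed women. That is fair as far as it goes. It still gives neither the amount of use nor the mix, so it cannot attribute a change in VTE to a change in use.

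Third, the illustration is stylised. It models all users, borrows a UK share, and case B needs an unexplained fall of about 21% in non-user risk (1 − 1.58/2). Granted; the numbers only make visible a point that holds by logic.

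Finally, a reader might count the lack of Danish VTE rates by type or generation as a second error. The documents do not support that. Objective 4 names no progestogen type, WP7 in section 9.2 allows different strategies by country, and further strata can be left to an analysis plan.

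**Conclusion.** The concern holds in a limited form. The WP5 association step is wrong as written: its stated purpose needs a measure of CHC use, and both of its inputs are VTE rates. It also contradicts the abstract, whose version is the sound one. The conclusion rests on the wording of the two sections. The scenarios in the working show that the WP5 pair of rates can be identical with and without a change in use, under assumed shares of use and rates taken from the protocol's risk table. WP2, WP7 and the abstract soften the consequence, so this is a correction that should be made before the Danish analysis and no threat to the study as a whole. The missing generation-specific Danish VTE rates are a possible improvement only.

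**What to change.** **Correction.** Replace the WP5 association sentence with: *The change between the two windows in age-standardised VTE incidence (all women, and initiators/switchers) will be compared with the change between the windows in age-standardised CHC initiation rates and in the generation shares of initiators from WP2.* Add that, with two windows, the comparison is ecological and descriptive. Leave the abstract's comparator as it is.

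The cost is wording, plus tabulating the WP2 initiation rates by window and age-standardising them, since section 9.2 plans them by calendar year. No new data are needed.

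**Optional improvement.** As in WP4 and WP6, also report Danish VTE incidence per window by CHC generation. WP2 already obtains dispensing date, ATC code, defined daily dose and amount. Count person-time on the product, or within one year of initiation as WP4 does, because WP5 follow-up does not end when a woman stops or switches. The cost is an exposure-time rule and some programming.

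The drawback is precision. Splitting the 480 cases by window length (25 and 23 months) gives 250 and 230. For a generation with half the cases (125 and 115), the 95% interval for the between-window rate ratio extends by a factor of exp(1.96 × √(1/125 + 1/115)) = 1.29 either way. With a fifth of the cases (50 and 46) the factor is 1.49. Initiators and switchers are a subset that the protocol does not size, so intervals for them would be wider still, and the data would say little about changes within a generation.
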